Resting State. Participants will also be asked to rest for 6 minutes while functional data is being collected to assess resting state activation.

6.6.2. Proton MRS: GABA-edited spectra will be acquired using the MEGA-PRESS experiment, from 1 voxel (medial frontal). 9 minutes duration. Spectra will be analyzed using the Gannet package for the batch analysis of GABA-edited MR spectra, quantifying GABA concentration relative to water, correcting for voxel CSF fraction. OFF spectra will also be analyzed using LCModel to give concentrations for additional metabolites NAA, Glx, Cho, MI, and Cr. Analyses. Cerebral MRS metabolite concentrations will be derived from spectral analysis²⁹⁵ With unsuppressed water FID at TE=30ms used for eddy-current correction. Time domain MRS ratios will be derived normalized for Cr. A double-exponential decay will be fitted to the water amplitudes at the 7 echo times. The signal amplitudes of brain tissue and CSF will be derived (corrected for T2 decay), with brain water signal used to correct for partial CSF volume. MRS Quality Assurance: GABA-edited MR spectra will be visually screened, and additionally spectra with a fitting residual of over 10% will be accepted for further analysis. The concentration measures for the additional metabolites will be accepted with an LCModel Cramer-Rao lower bounds (%SD) of less than 20%, a reliable estimate for a particular metabolite for group comparisons²⁹⁵. Scans resulting in spectra that do not meet quality criteria will be repeated. Past studies showed intra-subject variability of ~10% for GABA and 3-5% for other MRS peaks. Line width and signal-to-noise resonance ratios are plotted over time (brain, phantom) to monitor spectral

quality; inter- and intra-subject variability assessed by correlation and Bland and Altman plots.^{412,413}

6.6.3. Structural MRI. High-resolution whole brain axial gradient-echo MPRAGE 3-D T1-weighted images will be acquired for volumetric and cortical thickness analyses and fMRI. Analyses: Volumetric indices will be obtained for total gray and white matter, FreeSurfer ROIs²⁹⁶⁻²⁹⁸, and a priori ROIs (MRS, fMRI).

6.6.4. FLAIR. Fluid attenuated inversion recovery (FLAIR) images will be acquired to assess white matter hyperintensity load (i.e., white matter damage). Volumetric and whole brain analyses of data will be used to look at region specific versus global levels of white matter load.

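### The GABA fitting-residual rule is written backwards: residuals over 10% are accepted, so GABA has no working numeric quality limit

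*Combined protocol and SAP*

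**What the plan says.** Section 6.6.2 sets the acceptance rules for the spectroscopy data.

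- **GABA, first condition:** "GABA-edited MR spectra will be visually screened". No threshold is attached.
- **GABA, second condition:** "spectra with a fitting residual of over 10% will be accepted for further analysis".
- **Other metabolites (NAA, Glx, Cho, MI, Cr, taken from the OFF spectra):** their concentrations "will be accepted with an LCModel Cramer-Rao lower bounds (%SD) of less than 20" per cent.
- **Consequence of failure:** "Scans resulting in spectra that do not meet quality criteria will be repeated".
- **Monitoring:** "Line width and signal-to-noise resonance ratios are plotted over time", and variability is examined by correlation and Bland-Altman plots. Neither comes with an accept-or-reject limit.
- **Repeatability:** "Past studies showed intra-subject variability of ~10% for GABA and 3-5% for other MRS peaks".

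The GABA fit comes from the "Gannet package for the batch analysis of GABA-edited MR spectra". The section does not say whether the residual is known while the participant is still available for a repeat scan.

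**The concern.** A larger residual means that the fitted model describes the spectrum less well. A rule that accepts a spectrum because its residual exceeds a limit therefore selects in the wrong direction. The Cramer-Rao rule in the next sentence runs the expected way, but it covers only the other metabolites.

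An acceptance rule decides which values enter the analysis. H2.2 (section 5) predicts a long-term rise in GABA and modulation of GABA in frontal areas. The abstract's third hypothesis uses GABA as a predictor of individual response to tDCS. If the sentence is followed, poorly fitted GABA values that pass the visual screen enter both analyses. If staff silently ignore it, the protocol does not record the rule that was used, and inclusion of GABA values could be settled after the data have been seen.

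**Working it through.** The documents derive no figure from the 10% threshold, so there is no plan figure to reproduce. The check is one of logic, followed by simple counts for scope.

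**1. Apply the rule to example residuals.** The residuals of 5%, 12% and 40% are illustrations, not data. Each spectrum is assumed to pass the visual screen.

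| Residual | As written, strict (over 10% is required) | As written, permissive (over 10% is an extra route in) | Direction reversed, 10% kept |
|---|---|---|---|
| 5% | not accepted, scan repeated | not excluded by the rule | accepted |
| 12% | accepted | accepted | rejected |
| 40% | accepted | accepted | rejected |

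The strict reading keeps the worse fits and repeats the better one. The permissive reading excludes nothing for poor fit. Under both, no numeric limit removes a badly fitted GABA spectrum.

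**2. Look for another numeric limit that covers GABA.**

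- The Cramer-Rao bound below 20% applies to NAA, Glx, Cho, MI and Cr, not to GABA.
- Line width and signal-to-noise are plotted without a cut-off.
- The variability of about 10% describes past studies and is not an acceptance limit.
- The repeat-scan sentence refers back to the quality criteria, so for the residual it inherits the inversion.

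Working numeric criteria: one for the other metabolites, none for GABA.

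**3. Reach.**

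- H2.2 names GABA, NAA, Cho and MI. The rule governs 1 of these 4.
- Stated intra-subject variability, GABA against the other peaks: 10/5 = 2.0 and 10/3 = 3.3. GABA is thus 2.0 to 3.3 times as variable. This is repeatability, not fitting residual, and it is not an effect size.
- GABA spectra governed at full attendance: 90 participants × 3 imaging visits (section 6.1) × 1 voxel (section 6.6.2) = 270. If GABA is acquired in both regions named in section 6.2.1, the count is 90 × 3 × 2 = 540. The finding does not depend on which applies.

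**4. What cannot be computed.** The documents give no distribution of residuals, no expected GABA effect and no power calculation. The bias or loss of precision in the GABA analyses therefore has no calculable value, and no share of failing spectra is assumed here.

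**The case against.** The strongest reply is that this is an obvious slip which no spectroscopy analyst would follow. Taken strictly, it would mean repeating nine-minute acquisitions to obtain worse fits. The same paragraph shows the intended direction, nothing suggests that the literal rule was used, and all harm depends on someone following it. Section 7 also promises a manual of procedures covering quality assurance, which may hold the correct rule. Prediction of individual response is only a secondary aim, and section 7 calls the study exploratory.

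Much of this is fair and limits the weight of the point. It does not remove it. The manual is not among the documents and cannot correct the protocol text. The Bland-Altman plots set no acceptance limit. A reader still cannot tell which rule was applied, or whether 10% is the intended value once the direction is corrected.

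Two further points stand. The other metabolites have their own correctly directed rule, but their OFF spectra come from the same acquisition, so a repeat triggered by the GABA rule could change which OFF spectrum is analysed. And low repeatability does not show that residuals often exceed 10%; it shows only that GABA has less margin for a faulty check.

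**Conclusion.** The concern holds. The residual rule is wrong as written, and GABA is left with visual screening alone, without a stated threshold. Its reach is one of the four metabolites in H2.2, plus GABA as a predictor. The cognitive outcomes of Aim 1 are untouched, and the other metabolites are touched at most indirectly. The size of any effect on the GABA results is unknown and cannot be derived from the documents.

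The conclusion rests on the ordinary meaning of a fitting residual and on the text of section 6.6.2. That 10% is the right limit after reversal is an assumption for the sponsor to confirm. The sentence should be fixed before the GABA data are analysed, but it does not threaten the trial as a whole.

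**What to change.** - Reverse the sentence in section 6.6.2: a GABA spectrum with a residual above 10% is rejected; one at or below 10% is accepted only if it also passes the visual screen.
- Have the sponsor confirm both the direction and the 10% value.
- State that the repeat-scan provision applies to spectra that fail, and that a spectrum is excluded if its residual becomes known only at batch analysis.
- If spectra have already been processed, state which direction was applied. Only if it was the literal one, re-filter the archived data and report, by arm and visit, how many GABA values change status.

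The cost is a short text correction and one confirmation. Re-filtering would use the raw and processed imaging data that section 7 says are archived, and needs no new scans. Its real cost is that GABA values rejected at that stage become missing, because repeating the scan is no longer possible.

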Aim 1. Determine whether neurocognitive improvement and longer-term functional outcome (as measured by “ecological assessment”) are better when CT is coupled with tDCS, an intervention that will increase neural plasticity and augment training effects.

H1.1. Active tDCS combined with CT will amplify effects of CT on measures of attention, working memory, executive functioning, and learning efficiency, while sham tDCS will not.

H1.2. Active tDCS will enhance near and far transfer of CT, but sham will not evidence near or far transfer.

Aim 2. Determine whether CT combined with tDCS leads to greater functional and metabolic brain changes (fMRI, MRS). Effects will parallel Aim 1.

H2.1. Combined CT + tDCS will potentiate decrease activation in working memory and attentional (dorsolateral prefrontal cortex, medial frontal cortex, inferior parietal lobe, supplementary motor association cortex) brain systems, reflecting increased neural efficiency, while CT + sham tDCS will not.

H2.2 Cerebral metabolite alterations will occur secondary to CT and tDCS, with long-term increase in GABA and *N*-acetyl aspartate (NAA) concentrations, and decreased choline (Cho) and myoinositol (MI) concentrations in the frontal cortex and posterior parietal cortex. CT and tDCS will modulate MRS GABA in frontal areas. These effects will be specific to CT.

Secondary aim. We will examine which baseline factors (e.g., clinical, demographic, neuroimaging, cognitive) best predict individual differences in outcome.

6. Research Plan:

6.1. Experimental design. This study employs a randomized trial design with 90 participants. One factor with two levels [Factor 1 = stimulation type (active or sham)] yields two cells. Thus, participants will be assigned to one of two conditions:

1: Active tDCS + CT

2: Sham tDCS + CT

CT has previously been established with strong effects on cognitive and functional outcomes. Some small clinical trials showed small to medium effects of tDCS in conjunction with CT.

Participants will be assessed at three primary time points during the study, plus one screening visit on the front end to be sure they meet all inclusion criteria for the study:

- 1) Informed Consent and Screening Visit
- 2) Assessment Visit #1- baseline pre-training;
- 3) Assessment Visit #2- post-2 weeks
- 4) Assessment Visit #3- three month follow-up after all training
(see Figure below for summary).

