tasks. Training platform. CT employs a PositScience BrainHQ suite via its researcher portal. These tasks are web-based and multi-platform (i.e., Windows, Mac). Participants will be randomly assigned to training on 4 tasks focusing on working memory or 4 tasks focusing on attention/speed of processing. Participants will be required to have a specific viewing distances. Study interventionists will provide daily performance summaries. The rationale and task demands for each component were described earlier (A.3.3). These CT are commercially available (www.positscience.com), with well-documented protocols/manuals (See Appendix 1) and thus not described in detail here. (See miscellaneous attachments for specific game descriptions.)

Hardware

Participants will complete CT on computers located at Clinical Translational Research Building. Support: Participants will have the opportunity to ask questions, and will be instructed on the various computer tasks. No special technical skills or experience are required. A support phone number will be available if participants have questions arise between study visits.

6.5. Transcranial Direct Current Stimulation:

Bilateral Frontal tDCS: A Soterix Clinical Trials Direct Current Stimulator will apply 20 minutes of 2.0mA direct current through two biocarbon rubber electrodes encased in saline soaked 5cm² sponges (8cc of 0.9% saline solution) which then may be covered with electrode paste, and placed over the frontal cortices at F3 and F4 (10-20 system). Based on our well-established computational modeling workflow (C.4.1), F3/F4 stimulation delivers a broad pattern of frontal stimulation (see C.4.1d). Current inflow will occur on the right (F4), and outflow on the left (F3). Impedance quality will be $\leq 10\text{k}\Omega$ to insure proper stimulation of brain tissue.

Sham tDCS: Sham stimulation is performed with the same device and all procedures will be identical except for the duration of stimulation. Participants will receive 30 seconds of 2 mA of direct current stimulation at the beginning of the session.

Participants habituate to the sensation of tDCS within 30-60 seconds of stimulation. This procedure provides the same sensation of tDCS without the full duration of stimulation, making it a highly effective sham procedure. Blinding: The device has built in RCT double blinding protocols. Soterix will communicate only with [name] (Co-Mentor/statistician) to de-identify data for analyses.

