Protection against risks associated with neurocognitive tests. The neurocognitive assessments have minimal risk associated with them. Some participants experience stress associated with being tested, though this tends to be quite limited. Breaks will be given in those cases. Research staff that collect data have been trained in the conduct of all cognitive function tests by other senior staff members. Research staff members will be certified in the conduct of the cognitive function tests before they work with study participants.

Data and Safety Monitoring Plan:

A data and safety monitoring plan (DSMP) will be implemented to ensure the safety of all participants involved in the study and to ensure the validity and integrity of the data. The PI will be responsible for coordinating activities of the DSMP, including: arranging meetings and communications, and identifying and reviewing relevant participant materials. The data and safety information obtained on each study participant will be reviewed at weekly meetings. The primary goal of the DSMP will be to monitor the progress of the study and safety of participants and if necessary, recommend modifying the study or terminating the study as appropriate.

Concerns that might dictate modification or termination of the study include:

- Participant safety
- Outcome data
- Data quality
- Integrity
- Intervention efficacy
- Recruitment
- Performance

Both the PI and the study staff will review the study weekly and examine reports of adverse incidents and reports of study participant recruitment and follow-up. Throughout the course of the study, information regarding issues deemed critical to the study or to the safety of research participants will be provided to the PI and primary mentors. As a result of receiving this critical information, a meeting to discuss this information may be convened. Information deemed critical would include:

- Serious and non-serious adverse events that may occur
- Suspicion of scientific fraud or misconduct
- Any other issues which may warrant protocol changes or modifications.

Because this is an exploratory study with minimal risk associated with the proposed intervention and limited financial resources, there will not be an external data safety and monitoring board for this study. The research team, however, will follow the procedures for data safety and monitoring as required by the Institutional Review Board at the University of Florida (UF IRB).

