Data quality control. All staff involved in data collection will be trained and certified to ensure their competence, and re-certified periodically throughout the study as we have done in similar trials. Data will be collected and numerically coded using pre-tested electronic entry forms. At the time of collection, there will be initial clerical review of all
Protocol IRB #201400328
IRB version 03.09.04
PI version 5/13/2019

data for accuracy and completeness. Every effort will be made to ensure that missing data are kept to a minimum. Data entry programs with range checking and response validation will be used for all data entered. Under supervision from the PI, the data manager will conduct error checking procedures and preliminary analyses on all data to ensure their accuracy. The RAs will be trained to avoid omissions in data entry and computer entry protocols will be programmed to avoid accidental skipping of question items. We believe that the quality control system to be used will ensure a complete and accurate database, and maximize the likelihood that the intervention will be delivered correctly and efficiently. As we have done in prior studies, a manual of procedures will be developed during the initial study start-up period that explicitly describes the specific procedures related to intervention delivery, data collection, and quality assurance.

Frequency of data review. Relevant data and safety information obtained on each study participant will be verified against the original source documents by the primary study coordinator on a bi-weekly basis. As noted above, any identified discrepancies will be discussed with the Principal Investigator and reviewed at weekly meetings.

Measurement and reporting of participant accrual and adherence to eligibility criteria. Review of the rate of participant accrual, adherence to inclusion/exclusion criteria will occur weekly during the recruitment phase and then every month to assure that participants meet eligibility criteria and ethnic diversity goals outlined in the grant proposal.

Designation of an independent monitoring committee. The Independent Monitoring Committee for this study will consist of an established board which has reviewed all studies conducted within the CAM-CTRP during bi-annual conference calls for the past six years.

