Safety Review Plan Study progress and safety will be reviewed monthly (and more frequently if needed) by the principal investigator. Progress reports, including participant recruitment, retention/attrition, and AEs will be provided the IoA Independent Monitoring committee for bi-annual reviews. An annual report will be compiled and will include a list and summary of AEs. In addition, the annual report will address (1) whether adverse event rates are consistent with pre-study assumptions; (2) reason for dropouts from the study; (3) whether all participants met entry criteria; (4) whether continuation of the study is justified on the basis that additional data are needed to accomplish the stated aims of the study; and (5) conditions whereby the study might be terminated prematurely. The annual report will be signed by the chair of the Independent Monitoring Committee and may be forwarded to the IRB, NIH, & CTSI. The IRB and other applicable recipients will review progress of this study annually.

Final storage of paper data. All paper data (e.g., consent forms) will be housed at a facility that specializes in the storage of medical/ research information. The destruction date of these files will be at least 7 years from the termination of the study and will be authorized by the Principal Investigator of the research study.

Access to cleaned computer data. Once the study is complete, and all data have been collected, entered and passed the audit process, the data will be available to the Principal Investigator and his designates for analysis. Only the Principal Investigator can

give permission for the release of aggregated study data. No confidential information may be released without the express written consent of the study participants. Only copies of the finalized data will be released. The original data file will remain in its pristine state.

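### Does listing outcome data and efficacy as grounds to modify or stop the trial open an uncontrolled interim efficacy analysis?

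*Combined protocol and SAP*

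**What the plan says.** The Data and Safety Monitoring Plan in Section 7 opens its list with "Concerns that might dictate modification or termination of the study include". The seven items include outcome data and "Intervention efficacy", next to safety, data quality, integrity, recruitment and performance. The plan can recommend modifying or ending the study, and "The PI will be responsible for coordinating activities of the DSMP".

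Other text bears on whether an efficacy look could take place:

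- **Scheduled reviews.** The weekly review by the PI and staff covers adverse incidents, recruitment and follow-up. The monthly PI review covers progress and safety. For the twice-yearly committee review, "Progress reports, including participant recruitment, retention/attrition, and AEs will be provided" to the Independent Monitoring Committee. An annual report, signed by that committee's chair, covers whether continuation is justified by the need for more data to meet the aims, and the conditions for early termination.
- **Release of data.** The paragraph headed Access to cleaned computer data sets the timing: "Once the study is complete, and all data have been collected, entered and passed the audit process, the data will be available". Those who then receive them are the PI and designates.
- **Blinding (Section 6.5).** "The device has built in RCT double blinding protocols. Soterix will communicate only with" the co-mentor/statistician, for de-identification.
- **Data checks (Data quality control).** The data manager, supervised by the PI, runs "preliminary analyses on all data to ensure their accuracy".

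No section states a significance level, a look schedule for outcomes, a boundary, a futility rule or a named reader of by-arm results. No section states that there will be no interim efficacy analysis.

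**The concern.** Efficacy and outcome data are listed separately from safety and data quality, so they cannot be dismissed as safety items under another name. A ground for stopping that has no rule attached is normally a warning sign. If someone compared the arms during the trial and could stop on a good result, the type I error would exceed its nominal level and the estimated effect would be biased upward. Section 8 presents the data as groundwork for larger studies, so an inflated estimate could carry into their planning. Because the plan names no one to read arm-level outcomes, the list also raises the question of whether the blind would hold.

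**Working it through.** The plan gives no alpha, power or boundary, so there is no figure of its own to reproduce. The check has two parts: the size of the harm if the feared look happened, and whether the plan leads to such a look.

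**1. Size, if it happened.** Assumptions, none of them from the plan: two-sided 5%, equally spaced looks, 45 per arm (90/2), one outcome with known SD of 1.

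*Type I error*, rejecting at |z| > 1.96 at any of K looks (K includes the final one), by numerical integration:

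| K | Type I error |
|---|---|
| 1 | 5.0% |
| 2 | 8.3% |
| 3 | 10.7% |
| 5 | 14.2% |
| 10 | 19.3% |

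If only a favourable result can stop the trial early, half the excess remains at K = 2, by symmetry: 0.0500 + (0.0831 − 0.0500)/2 = 0.0666.

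*Bias*, one look at half the data (22.5 per arm). The standard error is √(2/22.5) = 0.298, so any early stop for benefit needs an estimate above 1.96 × 0.298 = 0.58. Section 6.1 says "Some small clinical trials showed small to medium effects of tDCS in conjunction with CT"; taking this as d = 0.2 to 0.5, simulation gives:

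| True d | Mean estimate | Stops early for benefit | Mean estimate among those |
|---|---|---|---|
| 0.2 | 0.22 | 10% | 0.73 |
| 0.3 | 0.34 | 17% | 0.74 |
| 0.5 | 0.56 | 39% | 0.79 |

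*Futility only.* Stop if the half-way z is below 0; otherwise test at one-sided 0.025 at the end. The type I error is P(Z₁ ≥ 0, Z₂ > 1.96) with correlation √0.5. This is 0.0250 − 0.0003 = 0.0247, so there is no inflation.

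**2. Does the plan lead there?** The figures above 5% and the bias need three things together.

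- *An arm-level comparison during the trial.* No review has one among its stated contents. The PI and co-investigators can see raw data (Data entry requirements), but no section gives them allocation codes. Outcomes without codes are pooled outcomes.
- *A test on that comparison.* The preliminary analyses under Data quality control are for accuracy. Release for analysis comes after completion and audit.
- *A favourable result that triggers action.* The list is of concerns. Lack of efficacy is naturally a concern; success is not. No section describes a stop for benefit.

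The two items still have a harmless use. Both arms receive cognitive training (Section 6.1), and Section 6.2.1 treats training as the primary intervention on which stimulation is tested. Pooled data could show no training gain, floor or ceiling effects, or missing outcomes. Any of these is a fair reason to reconsider the study without unblinding anyone.

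**The case for a change.** The best case for acting is that the text does not close the door. The release rule is headed for cleaned data and does not cancel the list. The PI, co-investigators and research assistants have access to forms and stored data. The preliminary analyses are not said to be pooled. The annual report must address continuation and early termination in relation to the aims, yet no termination conditions are written down. Section 5 calls the trial adaptive without giving an adaptation rule. A few words would settle all this at almost no cost.

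Much of this is accurate as a reading of the text: the interim policy is unwritten, and an explicit sentence would be tidier. What does not stand is the step to a defect in the inference. Access to uncoded data is not access to arm results, and a duty to discuss continuation is not a duty to test efficacy. The view that the efficacy item must either be inoperative or require unblinding overlooks pooled review.

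Two neighbouring points are separate matters of wording. One is the adaptive label. The other is the statement that there is no external board beside the text designating an Independent Monitoring Committee. Neither creates an efficacy look.

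**Conclusion.** The observation is accurate but does not call for a change. Followed as written, the plan contains no interim between-arm efficacy test, so its type I error and effect estimate are not affected. The conditional figures (8.3% at two looks, 19.3% at ten, and mean estimates above 0.7 after an early stop for benefit) describe a procedure that no section sets out. They also measure inflation over a significance level that the plan never states.

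The gap is one that a trial team fills sensibly: keep in-trial review to safety, conduct and pooled data, and analyse by arm at the end. The release rule and the blinding arrangement already point that way. The conclusion assumes that the blind in Section 6.5 holds until completion and that no arm-level efficacy test is run before then. If one were run, the number and timing of looks would have to be reported and the inference adjusted.
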